7.8 Product Receipt and Tracking

Sites with these clinically labeled products will track disposition upon receipt or return of the products, as well as upon implant or explant of the product. Tracking includes dates and quantities received, used, explanted and returned. Lot/serial numbers and expiration dates will be documented and used for traceability. All of these elements will be entered on an electronic Case Report Form (eCRF).

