10.3 Scheduled Visit Windows

Medtronic will provide the target dates and windows for each visit to the study site, as applicable. Should a subject miss a visit or the visit fall outside the pre-specified window, a study deviation must be reported and the original visit schedule maintained for subsequent visits. A late visit is preferred over a missed visit but must be accompanied by a study deviation. Visit windows are listed in Table 6.

Table 6: Data collection and study procedure requirements at subject visits

Visit	Visit ranges
Enrollment/Baseline	Not applicable
Device Trial	≤ 28 days after Enrollment/Baseline
Device Trial Phone Calls	Daily, as needed
Device Trial Lead Explant	≤ 10 days from Device Trial
SCS Implant	≤ 60 days after end of Device Trial
Phone Calls	Weekly starting after Device Activation through the 3-Month Visit and monthly thereafter with an exception for the weeks or months when the subject has a study required visit.
Device Activation (Day 0)	9-16 days after implant: pending wound healing
[REDACTED]	[REDACTED]
Randomization and In-clinic Testing	30 days ± 5 days from Day 0 (visit may occur on the same day as Visit 4 if Visit 4 is occurring within window, and at the discretion of the PI)
3-Month	90 days ± 15 days from Day 0
6-Month	180 days ± 15 days from Day 0
12-Month	360 days ± 30 days from Day 0
18-Month	540 days ± 30 days from Day 0

Visit	Visit ranges
24-Month	720 days \pm 30 days from Day 0

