10.11 Device Trial Lead Explant

All subjects will have their device interrogated. All reports (final) will be collected and leads will be explanted. Trial lead explant must occur on or before 10 days from the trial implant. Subjects who have 50% or greater reduction in pain will go onto a permanent INS implant in the study. If not, exit the subject from the study.

The following information is required to be collected at the trial lead explant visit:

- [REDACTED]
- Collect data files via the clinician programmer tablet and securely send to Medtronic
- Pain medication changes
- AEs/device deficiencies

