10.20 System Modification

System modifications (e.g. lead or device revision, replacement, or explant) may occur in the study due to ineffective or loss of therapy, AEs, device deficiencies, or subject concerns that are not correctable by programming. In the event of a system modification, the visit schedule for the subject will remain unchanged. If the SCS device requires replacement, contact a member of the Medtronic study team as the decision to allow re-implant will be handled on a case-by-case basis. If the system is explanted, the explanted system will be returned to Medtronic. All explanted products should be returned to Medtronic for analysis when permissible by local laws and regulations. See Sections 7.10 and 7.11 for final product disposition details.

The following information is required to be collected during system modification visits:

- Changes to the implanted system
- Collect data files via the clinician programmer tablet and securely send to Medtronic
- Fluoroscopy/x-ray, if necessary
- Pain medications
- AEs/device deficiencies

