10.25 Subject Exit, Withdrawal or Discontinuation

10.25.1 Study Exit

A study exit eCRF is required for all subjects. Prior to exiting a subject from the study, it is recommended to follow the subject until all ongoing system and/or procedure related AEs are resolved or unresolved

with no further actions planned, or until official study closure, whichever occurs first. Following exit, subjects will continue to receive standard medical care as they would have received a commercially available SCS device and be followed per Investigator discretion. Upon exiting from the study, no further study data will be collected or study visits will occur for the subject. All data available through the time of the subject's exit will be used for analysis.

Subjects are urged to remain in the study as long as possible but may be exited from the study for any of the following situations:

- Study completed
- Subject lost to follow-up
- Subject death
- Subject did not meet inclusion/exclusion criteria
- Subject was not implanted with the study device
- Subject did not provide informed consent
- Subject chooses to withdraw (e.g., consent withdrawal, relocation to another geographic location)
- Investigator deems withdrawal necessary (e.g., medically justified, inclusion/exclusion criteria not met, failure of subject to maintain adequate study compliance)

Complete an Unscheduled Visit if the subject exits early, between visits and prior to the last study visit:

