12.6 Subject Death

All subject deaths must be reported by the investigator to Medtronic on an AE form (AE with outcome of fatal) as soon as possible after the investigator first learns of the death. In case of death, there should be only one AE with the outcome of death.

In the event of a subject's death, it is recommended that the implanted system be explanted and returned to Medtronic for analysis whenever possible per local process. Local laws and procedures must be followed where applicable. If any system component is returned to Medtronic, internal return product reporting systems may be used to gather additional information about the returned device/component.

A copy of the death certificate, if available and allowed by state/local law, should be sent to the Medtronic clinical study team. When a death occurs in a hospital, a copy of the death summary report and all relevant hospital records, if available should be sent to the Medtronic clinical study team. If an autopsy is conducted, a copy of the autopsy report should also be sent to the Medtronic clinical study team if available and allowed by state/local law. When the death occurs at a remote study site, it is the investigative study site's responsibility to attempt retrieval of information about the death. Additionally, device disposition information should be updated.

In summary, the following data will be collected:

- Date of death
- Detailed description of death
- Cause of death
- Relatedness to device, therapy and/or procedure
- Device interrogation information/reports (if available and allowed by state/local law)
- Device disposition information
- Death summary/hospital records (if available and allowed by state/local law)
- Autopsy report (if available and allowed by state/local law)
- Death certificate (if available and allowed by state/local law)

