7.10 Safety Evaluation

All device-related, therapy-related, and procedure-related adverse events (AE) and device deficiencies (DD) from the Device Trial Start Visit until study exit will be characterized in all subjects who started trialing and in all subjects who were implanted.

AEs and DDs will be coded and summarized overall and by location of pain using the most recent version of Medical Dictionary and Regulatory Affairs (MedDRA).

The AEs will also be categorized by relationship to study device and/or therapy. AEs will be presented in summary tables displaying the number of serious events, the number of events, and the number and percentage of subjects with one or more events. A summary of all device or therapy related AEs and of any deaths will also be provided. A narrative of each serious device- or therapy-related AEs will be provided.

DDs will be presented in summary tables displaying the number of deficiencies, and the number and percentage of subjects with deficiencies.

Device exposure will be summarized in those that started trialing from the ACS and the FAS and is considered from the time the subject is first exposed to the neurostimulation system (at the beginning of the device trial) until the product is explanted, or the subject discontinues from or completes the study, if later. Amount of exposure will be summarized (in months) using descriptive statistics such as mean, standard deviation, minimum, and maximum.

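### SAP 7.10 ends device exposure at the later of explant and study exit, so an explanted subject who stays in follow-up is credited with time without the device (minor; descriptive summary only)

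*SAP*

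**What the plan says.** SAP 7.10 (Safety Evaluation) starts device exposure at the beginning of the device trial and runs it "until the product is explanted, or the subject discontinues from or completes the study, if later". Exposure is summarized in months by mean, standard deviation, minimum and maximum, for subjects who started trialing and for the Full Analysis Set of implanted subjects. No other visible text defines exposure.

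Four protocol provisions decide how the rule works in practice:

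- Section 10.20 names explant among the system modifications and states: "In the event of a system modification, the visit schedule for the subject will remain unchanged". If the device needs replacing, "the decision to allow re-implant will be handled on a case-by-case basis".
- Section 10.25.1 lists the reasons for study exit, and explant is not among them. It adds: "Upon exiting from the study, no further study data will be collected or study visits will occur for the subject".
- Section 10.11 deals with subjects who do not reach the required pain reduction in the device trial: "If not, exit the subject from the study".
- Section 7.8 covers device records: "Tracking includes dates and quantities received, used, explanted and returned". These items are entered on an eCRF.

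**The concern.** Discontinuing and completing are mutually exclusive for one subject, so the qualifier *if later* cannot be choosing between them. It compares explant with study exit and takes the later date. An exposure measure should stop when the device is removed; this one does not stop if the subject is still in the study.

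The SAP introduction calls this a first-in-man study of the fully implantable device. The exposure summary is where a reader learns how long subjects carried it. Under the written rule, a subject explanted early who still attends the 24-Month Visit is indistinguishable from one who kept the device throughout.

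**Working it through.** The documents state no exposure figure, so there is nothing to reproduce. The check applies the SAP rule to the protocol's own visit timings.

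**Inputs.** From Protocol 10.3, Table 6:
- trial lead explant at most 10 days from the device trial
- implant "≤ 60 days after end of Device Trial"
- activation (day 0) 9 to 16 days after implant
- 24-Month Visit at day 720 ± 30

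The longest pre-activation period within the windows is 10 + 60 + 16 = 86 days. Explant days 90 and 360 are illustrations. One month is 30.44 days.

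**One subject who stays to the 24-Month Visit.**

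SAP exposure = max(explant day, exit day) + pre-activation days.
Time to explant = min(explant day, exit day) + pre-activation days.
Overcount = exit day − explant day, whatever the pre-activation period.

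| Explant day | SAP rule, exit day 720 | To explant | Overcount | Range over exit days 690 to 750 |
|---|---|---|---|---|
| 90 | 806 d (26.5 mo) | 176 d (5.8 mo) | 630 d (20.7 mo) | 600 to 660 d |
| 360 | 806 d (26.5 mo) | 446 d (14.7 mo) | 360 d (11.8 mo) | 330 to 390 d |

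A subject who exits 30 days after explant adds 30 days. One who exits at explant adds 0. A subject who fails the device trial is exited at trial lead explant, so the rule adds nothing there either.

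**Mean over implanted subjects (assumed rates).** Let r be the share explanted at day 90 and q the share of those who stay to day 720, with everyone else exiting at day 720. Neither value is in the documents. Mean overcount = r × q × 630.

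- q = 0: 0 days for any r.
- q = 0.5: 0.02 × 0.5 × 630 = 6.3 days, up to 0.15 × 0.5 × 630 = 47.3 days.
- q = 1: 0.02 × 630 = 12.6 days, up to 0.15 × 630 = 94.5 days.

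With 86 pre-activation days, the corrected mean is 806 − 630r. The q = 1 figures are then 12.6/793.4 = 1.6% and 94.5/711.5 = 13.3% of it. In the trialing set the effect is diluted. If all 140 enrolled subjects trial and 57 + 12 = 69 are implanted (also assumed), 94.5 days becomes 94.5 × 69/140 = 46.6 days.

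**Minimum and standard deviation.** Take the same stylized case with q = 1 and identical pre-activation periods. The SAP rule gives every implanted subject 806 days: minimum 806, SD 0. Time to explant gives a minimum of 176 days and an SD of 630 × √(r(1 − r)). That is 630 × √(0.02 × 0.98) = 88 days at r = 2% and 630 × √(0.15 × 0.85) = 225 days at r = 15%. A few early explants can therefore vanish from the minimum and spread even when the mean barely moves.

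**The case against.** **It is one descriptive line.** SAP 7.10 reports adverse events and device deficiencies as numbers of events and numbers or percentages of subjects, never per unit of exposure time. A reader might infer that safety rates are diluted by an inflated denominator; the visible plan contains no such rate. This stands and makes the point minor.

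**The interval matches the safety window.** SAP 7.10 characterizes events from the start of the device trial to study exit, so trial start to exit is a sensible quantity. That supports reporting it, under the name follow-up time. It does not make it device exposure.

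**Staying in the study after explant is inferred.** The unchanged visit schedule could mean only that dates are not reset after a revision, and Protocol 10.25.1 permits withdrawal by subject or investigator. This stands in part. Explant is expressly among the modifications that sentence covers and is not an exit reason, so staying is possible; how often it happens is unknown.

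**The explant date may still count.** A reader might infer that reported exposure always equals trial start to study exit. The documents do not support that. Protocol 12.3 urges continued follow-up of ongoing device or procedure events after early exit, so a later explant could become known, and there the SAP rule would add real device time. After a death, Protocol 12.6 says "it is recommended that the implanted system be explanted and returned to Medtronic for analysis", which could also move the end date later. The sound claim is narrower: an explant before exit never shortens exposure.

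**The trial-to-implant gap.** A reader might also count as an error the device-free interval of up to 60 days between trial lead removal and implant. The SAP openly starts the clock at the device trial, so this is a stated convention.

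**Conclusion.** The rule is wrong as written, and the consequence is minor. For an explanted subject who remains in follow-up, reported exposure includes exit day minus explant day without the device: 630 days (20.7 months) for explant at day 90 and 360 days (11.8 months) for explant at day 360, with exit at day 720. It is zero for a subject who exits at explant.

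The effect on the mean cannot be determined from the documents. The 0 to 95 days shown rests wholly on assumed explant rates of 2% to 15% at day 90 and assumed retention of none to all; the top figure should not be read as expected. The wording may be a slip for the earlier date, but a programmer following the text would code the later one. No efficacy result and no planned adverse event or device deficiency count or percentage changes.

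**What to change.** In SAP 7.10, replace *if later* with *whichever is earlier*. Exposure would then run from the start of the device trial to the earlier of (a) explant of the implanted system not followed by re-implant and (b) study discontinuation or completion. Naming the implanted system keeps trial lead removal from ending the count for subjects who go on to implant. The re-implant condition is needed because Protocol 10.20 allows re-implant case by case.

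If trial start to study exit is also wanted, to match the adverse event window, report it separately as follow-up time.

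The cost is one sentence in the SAP and, if follow-up time is kept, one more derived variable. Explant dates are already tracked on an eCRF under Protocol 7.8. The downside is slightly shorter reported exposure. Excluding the trial-to-implant gap, or splitting trial-phase from implant-phase exposure, is optional and not needed to correct the error.

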7.11 Health Outcomes Analyses

No Health Outcomes Analyses will be performed

7.12 Changes to Planned Analysis

Any deviations from this SAP will be described in the final study report, as appropriate.

8. Validation Requirements

Statistical programming code that affects the result of the main analysis (e.g., not including sensitivity or supporting analyses) for the primary objective shall be validated using Level I validation. Programming code that affects the result of the main analysis for the secondary objective shall be validated using at least Level II validation. In addition, those main statistical analyses that are planned for publication and have not been previously validated using at least Level II validation. The CIP deviation summary shall be validated using at least Level III validation and the high-level adverse event summary shall be validated using at least Level II validation. Additional measures where a confidence interval has been generated may need to be validated using at least Level II validation.

9. References

[Redacted reference text]

Buhi, E. R., Goodson, P., & Neilands, T. (2008). Out of Sight, Not Out of Mind: Strategies for Handling Missing Data. *Am J Health Behav*, 32(1), 83-92.

[Redacted reference text]

[Redacted reference text]

[Redacted reference text]

[Redacted reference text]

[Redacted reference text]

[Redacted reference text]

[Redacted reference text]

[Redacted]

[Redacted]

[Redacted]

[Redacted]

[Redacted]

[Redacted]
